10.7.2. Glossary of terms

Adverse event:	
Any untoward medical occurrence in a patient or clinical investigation participant, temporally associated with the use of a medicinal product, whether or not considered related to the medicinal product.
 
An AE can therefore be any unfavorable and unintended sign (including an abnormal laboratory finding), symptom, or disease (new or exacerbated) temporally associated with the use of a medicinal product. For marketed medicinal products, this also includes failure to produce expected benefits (i.e., lack of efficacy), abuse or misuse.

Blinding:	
A procedure in which 1 or more parties to the study are kept unaware of the intervention assignment in order to reduce the risk of biased study outcomes. The level of blinding is maintained throughout the conduct of the study, and only when the data are cleaned to an acceptable level of quality will appropriate personnel be unblinded or when required in case of a serious adverse event.
 
In an open-label study, no blind is used. Both the investigator and the participant know the identity of the intervention assigned.

Caregiver:	
A ‘caregiver’ is someone who:
 
• Lives in the close surroundings of a participant and has a continuous caring role or• Has substantial periods of contact with a participant and is engaged in his/her daily health care (e.g., a relative of the participant, a nurse who helps with daily activities in case of residence in a nursing home). 
In the context of this study, a caregiver can be appointed by the participant to oversee and support the participant’s compliance with protocol-specific procedures (such as transcribing responses to eDiaries, receiving phone calls, planning study visits, etc.). However, at no time, the caregiver should evaluate the participant’s health status while completing eDiaries or make decisions on behalf of the participant.

Certified copy:	A copy (irrespective of the type of media used) of the original record that has been verified (i.e., by a dated signature or by generation through a validated process) to have the same information, including data that describe the context, content, and structure, as the original.
Eligible:	Qualified for enrollment into the study based upon strict adherence to inclusion/exclusion criteria.
Enrollment:	The process of registering a participant into a clinical study by assigning participant identification number after signing the ICF.
Essential documents:	Documents which individually and collectively permit evaluation of the conduct of a study and the quality of the data produced
eTrack:	GSK's tracking tool for clinical studies.
Evaluable:	Meeting all eligibility criteria, complying with the procedures defined in the protocol, and, therefore, included in the per protocol analysis.
Immunological correlate of protection:	A correlate of risk that has been validated to predict a certain level of protection from the targeted endpoint.
Intercurrent medical condition:	A condition that has the capability of altering the immune response to the study vaccine or is confirmed to have an alteration of the participant's initial immune status.
Intervention:	Term used throughout the clinical study to denote a set of investigational product(s) or marketed product(s) or placebo intended to be administered to a participant.
Intervention number:	A number identifying an intervention to a participant, according to intervention allocation.
Investigational vaccine:	A pharmaceutical form of an active ingredient being tested in a clinical study, including a product with a marketing authorization when used in a way different from the approved form, or when used for an unapproved indication, or when used to gain further information about an approved use.
	Synonym: Investigational Medicinal Product

Investigator:	A person responsible for the conduct of the clinical study at a study site. If a study is conducted by a team of individuals at a study site, the investigator is the responsible leader of the team and may be called the principal investigator. The investigator can delegate study-related duties and functions conducted at the study site to qualified individual or party to perform those study-related duties and functions
Participant:	Term used throughout the protocol to denote an individual who has been contacted to participate or who participates in the clinical study as a recipient of the study intervention (vaccine(s)/product(s)/control). Synonym: subject
Participant number:	A unique identification number assigned to each participant who consents to participate in the study.
Primary completion date:	The date that the final participant was examined or received an intervention for the purpose of final collection of data for all primary outcomes, whether the clinical study was concluded according to the pre-specified protocol or was terminated.
Protocol amendment:	The International Council on Harmonization (ICH) defines a protocol amendment as: 'A written description of a change(s) to or formal clarification of a protocol.' GSK further details this to include a change to an approved protocol that affects the safety of participants, scope of the investigation, study design, or scientific integrity of the study.
Protocol administrative change:	A protocol administrative change addresses changes to only logistical or administrative aspects of the study.
Randomization:	Process of random attribution of intervention to participants to reduce selection bias.
Remote visit:	This term refers to the visit conducted in the place other than the study site.
Self-contained study:	Study with objectives not linked to the data of another study.
Solicited event:	Events to be recorded as endpoints in the clinical study. The presence/occurrence/intensity of these events is actively solicited from the participant or an observer during a specified follow-up period following study intervention administration.

Source data:	All information in original records and certified copies of original records of clinical findings, observations, or other activities in a clinical study necessary for the reconstruction and evaluation of the study. Source data are contained in source documents (original records or certified copies).
Source documents:	Original legible documents, data, and records (e.g., hospital records, clinical and office charts, laboratory notes, memoranda, participants' diaries or evaluation checklists, pharmacy dispensing records, recorded data from automated instruments, copies or transcriptions certified after verification as being accurate copies, microfiches, photographic negatives, microfilm or magnetic media, x-rays, participant files, and records kept at the pharmacy, laboratories and at medico-technical departments involved in the clinical study).
Study intervention:	Any investigational or marketed product(s) or placebo intended to be administered to a participant during the study.
Unsolicited adverse event:	Any AE reported in addition to those solicited during the clinical study. Also, any 'solicited' symptom with onset outside the specified period of follow-up for solicited symptoms will be reported as an unsolicited adverse event.

1. INTRODUCTION

The purpose of this SAP is to describe the planned analyses to be included in the clinical study report (CSR) for Study RSV OA=ADJ-017 (218350). Details of the planned analysis are provided.

1.1. Objectives, Estimands and Endpoints

Objectives	Endpoints and Estimands
Primary	

 To demonstrate the non-inferiority of the FLU vaccine when co-administered with the RSVPreF3 OA investigational vaccine compared to the FLU vaccine administered alone. 	
 HI antibody titers for each of the FLU vaccine strains expressed as group GMT ratio, one month after the FLU vaccine dose.

 To demonstrate the non-inferiority of the RSVPreF3 OA investigational vaccine when co-administered with the FLU vaccine compared to the RSVPreF3 OA investigational vaccine administered alone. 	
 RSV-A neutralization antibody titers expressed as group GMT ratio, one month after the RSVPreF3 OA investigational vaccine dose.

 To demonstrate the non-inferiority of the RSVPreF3 OA investigational vaccine when co-administered with the FLU vaccine compared to the RSVPreF3 OA investigational vaccine administered alone. 	
 RSV-B neutralization antibody titers expressed as group GMT ratio, one month after the RSVPreF3 OA investigational vaccine dose.
Secondary	

 To evaluate the non-inferiority of the FLU vaccine when co-administered with the RSVPreF3 OA investigational vaccine compared to the FLU vaccine administered alone. 	
 HI seroconversion status for each of the FLU vaccine strains expressed as SCR between groups, one month after the FLU vaccine dose.

 To evaluate the humoral immune response to the RSVPreF3 OA investigational vaccine when co-administered with the FLU vaccine or administered alone. 	
 RSV-A neutralization antibody titers expressed as MGI at one month after the RSVPreF3 OA investigational vaccine dose. RSV-B neutralizing antibody titers expressed as MGI at one month after the RSVPreF3 OA investigational vaccine dose.

 To evaluate the humoral immune response to the FLU vaccine when co-administered with the RSVPreF3 OA investigational vaccine or administered alone. 	
 HI antibody titers for each of the FLU vaccine strains expressed as GMT, at Day 1 and Day 31. HI seroconversion status for each of the FLU vaccine strains expressed as SCR, from Day 1 to Day 31. HI seroprotection status for each of the FLU vaccine strains expressed as SPR, at Day 1 and Day 31. HI antibody titers for each of the FLU vaccine strains expressed as MGI, one month after the FLU vaccine dose.

 To evaluate the safety and reactogenicity following administration of the RSVPreF3 OA investigational vaccine and the FLU vaccine, co-administered or administered alone. 	
 Percentage of participants reporting each solicited event with onset within 7 days after vaccine administration (i.e., the day of vaccination and 6 subsequent days). Percentage of participants reporting unsolicited AEs (pIMD, non-serious AE or serious AE) within 30 days after vaccine administration (i.e., the day of vaccination and 29 subsequent days).

Objectives	Endpoints and Estimands
CCI	
 Percentage of participants reporting SAEs after vaccine administration (Day 1) up to study end (6 months after last vaccination). Percentage of participants reporting pIMDs after vaccine administration (Day 1) up to study end (6 months after last vaccination).

FLU vaccine refers to FLU aQIV

AE = adverse event; **CCI** [REDACTED]; **GMT** = geometric mean titer; **HI** = hemagglutination inhibition; **MGI** = mean geometric increase; **pIMD** = potential immune-mediated disease; **RSVPreF3 OA** = respiratory syncytial virus PreFusion protein 3 older adult; **SAE** = serious adverse event; **SCR** = seroconversion rate; **SPR** = seroprotection rate; **MG** = geometric mean of the within participant ratios of the post-dose titer over the pre-dose titer. **SCR** = percentage of vaccinees who have either a HI pre-dose titer $< 1:10$ and a post-dose titer $\geq 1:40$ or a pre-dose titer $\geq 1:10$ and at least a 4-fold increase in post-dose titer. **SPR** = percentage of vaccinees with a serum HI titer $\geq 1:40$ that usually is accepted as indicating protection.

Primary estimand

The primary clinical question of interest is to show non-inferiority of the RSVPreF3 OA investigational vaccine and the FLU vaccine when co-administered versus separate administration 1 month apart in eligible participants who complied with the study requirements as defined Per Protocol (refer to Section 3 for the definition of the Per Protocol Set [PPS] used for the primary analysis and to Section 4.2.2 for the statistical method).

1.2. Study Design

Overview of Study Design and Key Features	

Randomization 1:1 Total N = ~1028
 
Visit Timepoint
 
Co-Ad group N = ~514
 
Control group N = ~514
 
Vaccination Phase
 
Visit 1 Day 1
 
Visit 2 Day 31
 
CC1
 
Visit 4 Day 61
 
Contact 1 6 months post-last vaccination
 
RSV + flu vaccines
 
Flu vaccine
 
RSV vaccine
 
Safety monitoring
 
Solicited AEs up to 7 days post-dosing Unsolicited AEs up to 30 days post-dosing All SAEs and pIMDs up to study end SAEs related to study participation or to a concurrent GSK medication/vaccine up to study end AEs/SAEs leading to withdrawal from the study up to study end
 
CC1 : Blood sample (10 ml each visit for humoral immunogenicity)
 
CC1 : Contact with the participant (via phone, email, ...)
 
Visit CCI & CC1 Day 61 not applicable for the Co-Ad group
	
Vaccination Phase
 
Safety Follow-up
 
Safety monitoring
 
AE = adverse event; N = number of participants; pIMD = potential immune-mediated disease; RSV = respiratory syncytial virus; SAE = serious adverse event

Design Features
 
 Type of study: self-contained. Experimental design: Phase III, randomized (ratio 1:1), open-label, multi-country study with 2 parallel groups. Study groups: 
 Co-Ad (co-administration) group: Participants receiving the RSVPreF3 OA investigational vaccine co-administered with FLU aQIV (referred to as FLU vaccine). Control group: Participants receiving the FLU aQIV (referred to as FLU vaccine) and the RSVPreF3 OA investigational vaccine in a sequential manner. Duration of the study: ~6 months for participants in Co-Ad group; ~7 months for participants in Control group. Primary completion date: Day 61 (1 month after the RSVPreF3 OA investigational vaccine dose in Control group). Control: active comparator, i.e., sequential administration of licensed FLU vaccine and RSVPreF3 OA investigational vaccine. Blinding: open-label. Vaccination schedule: 
 Co-Ad group: Participants will be receiving both the RSVPreF3 OA investigational vaccine and FLU vaccine at Visit 1 (Day 1). Control group: Participants will be receiving the FLU vaccine at Visit 1 (Day 1) and subsequently the RSVPreF3 OA investigational vaccine at Visit 2 (Day 31). 	
Final analysis
 
End-of-Study analysis

Overview of Study Design and Key Features				
Study intervention	Study Groups	Number of Participants	Age (Min-Max)	Study Interventions
	Co-Ad	~514	≥ 65 years	RSVPreF3 OA investigational vaccine FLU aQIV
	Control	~514	≥ 65 years	RSVPreF3 OA investigational vaccine FLU aQIV
Co-Ad = co-administration; RSVPreF3 OA = respiratory syncytial virus PreFusion protein 3 older adult				
Interim Analysis	No interim analysis is planned			

2. STATISTICAL HYPOTHESES

The study includes the following confirmatory primary objectives.

- To demonstrate the non-inferiority of FLU vaccine when co-administered with the RSVPreF3 OA investigational vaccine compared to FLU vaccine administered alone in terms of HI GMT ratio for each of the FLU vaccine strains at 1 month after the FLU vaccine (i.e., at Day 31 [Visit 2] for both groups).

Null hypothesis vs. Alternative hypothesis:

$$H_0: \mu_{\text{Control group}} - \mu_{\text{Co-Ad group}} > \log(1.5) \text{ vs. } H_a: \mu_{\text{Control group}} - \mu_{\text{Co-Ad group}} \leq \log(1.5)$$

where μ represents the estimated mean of log transformed HI antibody titers at 1 month after the FLU vaccine dose. The null hypothesis will be rejected if the upper limit of the two-sided 95% CI for the group GMT ratio (Control group divided by Co-Ad group) in HI antibody titers for each of the FLU vaccine strains 1 month after the FLU vaccine ≤ 1.5

- To demonstrate the non-inferiority of RSVPreF3 OA investigational vaccine when co-administered with the FLU vaccine compared to RSVPreF3 OA investigational vaccine administered alone in terms of RSV-A neutralization antibody GMT ratio at 1 month after the RSVPreF3 OA investigational vaccine dose (i.e., at Day 31 [Visit 2] for the Co-Ad group and at Day 61 [Visit 4] for the Control group).

Null hypothesis vs. Alternative hypothesis:

$$H_0: \mu_{\text{Control group}} - \mu_{\text{Co-Ad group}} > \log(1.5) \text{ vs. } H_a: \mu_{\text{Control group}} - \mu_{\text{Co-Ad group}} \leq \log(1.5)$$

where μ represents the estimated mean of log transformed RSV-A neutralization antibody titers at 1 month after the RSVPreF3 OA investigational vaccine dose. The null hypothesis will be rejected if the upper limit of the two-sided 95% confidence interval (CI) for the group GMT ratio (Control group divided by Co-Ad group) in RSV-A neutralization antibody titers 1 month after the RSVPreF3 OA investigational vaccine dose ≤ 1.5 .

- To demonstrate the non-inferiority of RSVPreF3 OA investigational vaccine when co-administered with the FLU vaccine compared to RSVPreF3 OA investigational vaccine administered alone in terms of RSV-B neutralization antibody GMT ratio at

1 month after the RSVPreF3 OA investigational vaccine dose (i.e., at Day 31 [Visit 2] for the Co-Ad group and at Day 61 [Visit 4] for the Control group).

Null hypothesis vs. Alternative hypothesis:

$$H_0: \mu_{\text{Control group}} - \mu_{\text{Co-Ad group}} > \log(1.5) \text{ vs. } H_a: \mu_{\text{Control group}} - \mu_{\text{Co-Ad group}} \leq \log(1.5)$$

where μ represents the estimated mean of log transformed RSV-B neutralization antibody titers at 1 month after the RSVPreF3 OA investigational vaccine dose. The null hypothesis will be rejected if the upper limit of the two-sided 95% confidence interval (CI) for the group GMT ratio (Control group divided by Co-Ad group) in RSV-A neutralization antibody titers 1 month after the RSVPreF3 OA investigational vaccine dose ≤ 1.5 .

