9. STATISTICAL CONSIDERATIONS

9.1. Statistical hypotheses (Amended 13 December 2022)

Statistical hypotheses are associated with the confirmatory primary NI objectives, which will be tested sequentially to control overall Type I error.

Global type I error is controlled at 2.5% (1-sided).

The non-inferiority margins associated to each objective are provided in [Table 18](#).

Table 18 Study objectives and null hypothesis (Amended: 13 December 2022)

Objectives	Null hypothesis
Primary	
• To demonstrate the non-inferiority of the FLU vaccine when co-administered with the RSVPreF3 OA investigational vaccine compared to the FLU vaccine administered alone.	• True Group GMT ratio between the FLU vaccine (Control group) divided by the RSVPreF3 OA investigational vaccine when co-administered with the FLU vaccine (Co-Ad group) in HI antibody titers for each of the FLU vaccine strains one month after the FLU vaccine dose is above 1.5.
• To demonstrate the non-inferiority of the RSVPreF3 OA investigational vaccine when co-administered with the FLU vaccine compared to the RSVPreF3 OA investigational vaccine administered alone.	• True Group GMT ratio between the RSVPreF3 OA investigational vaccine (Control group) divided by the RSVPreF3 OA investigational vaccine when co-administered with the FLU vaccine (Co-Ad group) in RSV-A neutralization antibody titers one month after the RSVPreF3 OA investigational vaccine dose is above 1.5.
• To demonstrate the non-inferiority of the RSVPreF3 OA investigational vaccine when co-administered with the FLU vaccine compared to the RSVPreF3 OA investigational vaccine administered alone.	• True Group GMT ratio between the RSVPreF3 OA investigational vaccine (Control group) divided by the RSVPreF3 OA investigational vaccine when co-administered with the FLU vaccine (Co-Ad group) in RSV-B neutralization antibody titers one month after the RSVPreF3 OA investigational vaccine dose is above 1.5.

Co-Ad = co-administration; FLU vaccine refers to FLU aQIV; GMT = geometric mean titer; HI = hemagglutination inhibition; RSVPreF3 OA = respiratory syncytial virus PreFusion protein 3 older adult

Statistical testing of each endpoint will be organized sequentially to control overall Type I error.

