 - The UL of the 2-sided 95% CI on the Group GMT ratio (Control group divided by Co-Ad group) for RSV-A ***neutralizing antibody*** is ≤ 1.5 .
- Sequence 2:***
 - The UL of the 2-sided 95% CI on the Group GMT ratio (Control group divided by Co-Ad group) for RSV-B ***neutralizing antibody*** is ≤ 1.5*

Testing will progress in sequence 2 only if the sequence 1 is a success, so that no further adjustment of alpha is required.

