4.2.1. Between groups assessment

- The 2-sided 95% CI for the group GMT ratio in terms of HI antibody titers for each of the FLU vaccine strains between RSVPreF3 OA investigational vaccine administered alone (Control group) over RSVPreF3 OA investigational vaccine when co-administered with the FLU vaccine (Co-Ad group) will be computed at 1 month after the FLU vaccine (i.e., at Day 31 [Visit 2] for both groups).
- The 2-sided 95% CI for the group GMT ratio in terms of RSV-A neutralizing antibody titers between RSVPreF3 OA investigational vaccine administered alone (Control group) over RSVPreF3 OA investigational vaccine when co-administered with the FLU vaccine (Co-Ad group) will be computed at 1 month after the RSVPreF3 OA investigational vaccine dose (i.e., at Day 31 [Visit 2] for the Co-Ad group and at Day 61 [Visit 4] for the Control group).
- The 2-sided 95% CI for the group GMT ratio in terms of RSV-B neutralizing antibody titers between RSVPreF3 OA investigational vaccine administered alone (Control group) over RSVPreF3 OA investigational vaccine when co-administered with the FLU vaccine (Co-Ad group) will be computed at 1 month after the

RSVPreF3 OA investigational vaccine dose (i.e., at Day 31 [Visit 2] for the Co-Ad group and at Day 61 [Visit 4] for the Control group).

The results will be presented in tables as well as graphs using forest plots.

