4.2.2. Main analytical approach

The 2-sided 95% CI for group adjusted GMT ratio will be derived from **an ANCOVA model on \log_{10} transformed titer**. The model will include the treatment group and age category (age at vaccination: 65-69, 70-79 or ≥ 80 years) as fixed effects, and the pre-dose \log_{10} -transformed titer as covariate. Missing data will not be replaced. Titers below the assay cut-off will be replaced by half the assay cut-off, titers above the upper limit of quantification (ULOQ) will be replaced by the ULOQ.

Success criteria for non-inferiority and testing sequence:

The following testing sequence will be used:

1st sequence:

- The upper limit of the 2-sided 95% CI of the GMT ratio (Control group divided by Co-Ad group) for each of the FLU vaccine strains are ≤ 1.5 .

AND

- The upper limit of the 2-sided 95% CI of the GMT ratio (Control group divided by Co-Ad group) for RSV-A neutralization antibodies is ≤ 1.5 .

2nd sequence:

- The upper limit of the 2-sided 95% CI of the GMT ratio (Control group divided by Co-Ad group) for RSV-B neutralization antibodies is ≤ 1.5 .

Testing will progress in the 2nd sequence only if the 1st sequence is a success, so that no further adjustment of alpha is required.

Here is an example of SAS code that will be used:

```
proc mixed data=data_in;
  class agecat trt_grp;
  model log10(titer day x) = log10(pre_dose) agecat trt_grp;
  lsmeans trt_grp/cl pdiff alpha=0.05;
  run;
```

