4.8. Changes to Protocol Defined Analyses

No changes from the protocol defined analyses.

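### SAP Section 2 rejects the RSV-B primary null hypothesis on the RSV-A confidence limit, contradicting SAP 4.2.2 and Protocol 9.3.1

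*SAP*

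**What the plan says.** SAP Section 2 lists three confirmatory objectives, each with a null, an alternative, a definition of the parameter and a rejection rule. The third objective is RSV-B non-inferiority. Its parameter is defined correctly: μ "represents the estimated mean of log transformed RSV-B neutralization antibody titers". The next sentence then rejects this null when the following quantity has an upper 95% limit that does not exceed 1.5: "group GMT ratio (Control group divided by Co-Ad group) in RSV-A neutralization antibody titers 1 month after the RSVPreF3 OA investigational vaccine dose". The RSV-A objective just above it carries the same rule in the same words.

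The rule is stated on RSV-B elsewhere:

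- SAP 4.2.1, third bullet, plans to compute "The 2-sided 95% CI for the group GMT ratio in terms of RSV-B neutralizing antibody titers".
- SAP 4.2.2, second sequence, sets success on the ratio of Control over "Co-Ad group) for RSV-B neutralization antibodies is ≤ 1.5".
- Protocol 9.1, Table 18, gives the null as a true ratio "in RSV-B neutralization antibody titers one month after the RSVPreF3 OA investigational vaccine dose is above 1.5".
- Protocol 9.3.1, Sequence 2, uses "The UL of the 2-sided 95% CI on the Group GMT ratio (Control group divided by Co-Ad group) for RSV-B".

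The primary estimand text in SAP 1.1 refers the reader to Section 3 for the analysis set "and to Section 4.2.2 for the statistical method". SAP 4.8 states: "No changes from the protocol defined analyses".

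**The concern.** Protocol Amendment 1 promoted RSV-B from a secondary to a primary objective on the recommendation of CBER, and SAP amendment 1 was written to carry that change. A confirmatory endpoint needs one pre-specified decision rule that reads the same wherever it appears. Section 2 is where the SAP sets out the null, the alternative and the rejection condition together, and there the RSV-B condition names the wrong endpoint. SAP 4.8 rules out a deliberate departure from the protocol, so this is a contradiction within the SAP.

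Followed literally, RSV-B non-inferiority would be declared with no RSV-B data. The second step of the testing sequence would only repeat a condition already met in the first.

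**Working it through.** **Comparison of the texts**

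| Place | Endpoint that decides the RSV-B objective |
|---|---|
| SAP 2, objective and definition of μ | RSV-B |
| SAP 2, rejection sentence | **RSV-A** |
| SAP 4.2.1, third bullet | RSV-B |
| SAP 4.2.2, second sequence | RSV-B |
| Protocol 9.1, Table 18 | RSV-B |
| Protocol 9.3.1, Sequence 2 | RSV-B |

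Only the rejection sentence differs. It is complete and unredacted, and it belongs to the current text of SAP amendment 1.

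**Inputs** (Protocol 9.5, Table 21; SAP 5, Table 3): 462 evaluable per group; log10 SD 0.45 for RSV-A and RSV-B and 0.6 for each FLU strain; planned true ratio 1.05; margin 1.5; one-sided alpha 2.5%.

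**Reproducing the plan's figures**

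- Method: two-sample noncentral t with 922 df.
- Distance from planned ratio to margin: log10(1.5) − log10(1.05) = 0.1761 − 0.0212 = 0.1549.
- RSV: SE = 0.45 × √(2/462) = 0.0296; power 99.95% (stated 99.9%).
- FLU: the same formula with SD 0.6 gives 97.5% per strain (stated 97.5%).
- Global power: 1 minus the summed type II errors is 89.98% (stated about 90.0%).
- Enrollment: 462/(1 − 0.10) rounds up to 514 per group (stated 514).

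All agree. The power tables already treat RSV-B as a separate endpoint, so correcting the sentence changes none of them.

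**RSV-B tested on its own limit.** The CI half-width is a factor of 1.143, so RSV-B passes only if the observed ratio is at most 1.5/1.143 = 1.31.

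| True RSV-B ratio | P(upper limit ≤ 1.5) |
|---|---|
| 1.05 | 99.95% |
| 1.2 | 90.49% |
| 1.3 | 55.44% |
| 1.5 | 2.50% |

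**How often the two RSV limits disagree.** P(RSV-A passes at 1.05, RSV-B fails) = 0.9995 × (1 − P(RSV-B passes)), taking the two as independent:

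| True RSV-B ratio | Disagreement | Bounds over any correlation |
|---|---|---|
| 1.05 (plan) | 0.05% | 0 to 0.05% |
| 1.2 (assumed) | about 9.5% | 9.46 to 9.51% |
| 1.3 (assumed) | about 44.5% | 44.50 to 44.56% |

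**Adding the first step of the sequence.** RSV-B is reached only if all four FLU strains and RSV-A pass. At 97.5% per strain and assuming independence, the FLU condition multiplies by 0.975⁴ = 0.904. The last two rows become about 8.6% and 40%.

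**Worst case under the literal reading.** Put the true RSV-B ratio at the 1.5 margin and every other endpoint at 1.05. RSV-B would be declared non-inferior whenever the first step passes: 0.975⁴ × 0.9995, or about 90% under independence. On its own limit the probability is at most 2.5%.

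**The case against.** The strongest reply is that this is a copying slip with no operative effect. The estimand text sends the reader to SAP 4.2.2 for the method, and the criterion there is correct. The endpoint table, the planned CI, the power table and the protocol all treat RSV-B as its own endpoint, and SAP 4.8 settles any doubt in favor of the protocol. The sentence is not a workable rival rule either, because it would reject a statement about RSV-B without looking at RSV-B. At the plan's own ratio of 1.05 the two limits disagree in only 0.05% of trials. The larger percentages rest on ratios that appear nowhere in the documents, and they shrink somewhat once the FLU condition is included.

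Most of this stands. The intent is clear, the operative criterion is right, and the larger figures illustrate a literal reading; they do not predict what the analysts would do. None of it makes the sentence correct. It is the stated rejection rule for a primary hypothesis, and it names a different endpoint from the hypothesis it decides. A correction made before results are known needs no defense, whereas one made afterwards would.

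**Conclusion.** The concern holds. SAP Section 2 states the RSV-B rejection rule on the RSV-A limit, against its own definition of μ, SAP 4.2.1 and 4.2.2, and Protocol 9.1 and 9.3.1. It should be corrected, but it does not threaten the trial's validity: alpha, power (99.9% for RSV-B, about 90% overall) and the 514 per group are unaffected. An incorrect RSV-B conclusion would require someone to apply Section 2 in isolation. The disagreement rates assume the plan's SD of 0.45, 462 evaluable per group and a true RSV-A ratio of 1.05. The RSV-B ratios of 1.2 and 1.3 are assumptions. Correlation between the two RSV endpoints barely alters the rates.

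**What to change.** Before analysis, change RSV-A to RSV-B in the rejection sentence of the third objective in SAP Section 2, so that it matches SAP 4.2.2 and Protocol 9.3.1. This is a one-word text correction with no effect on data, programming or sample size. When the section is open, Section 2.1 could also refer to the testing sequence in 4.2.2 as the basis for type I error control. That cross-reference is optional, and the finding does not depend on it.
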